8.2 STUDY DESIGN

This is an open-label, multicenter, Phase I/II Dose Escalation study of repeated intratumoral injections of mRNA-2416 alone (Arm A) and in combination with intravenously administered durvalumab (Arm B) in patients with advanced relapsed/refractory solid tumor malignancies or lymphoma, followed by Expansion periods in patients with ovarian cancer in each treatment arm. The study includes the following 2 treatment arms:

- Arm A: mRNA-2416 alone
- Arm B: mRNA-2416 in combination with durvalumab (PD-L1 inhibitor)

Each arm of the study consists of a Dose Escalation and Dose Confirmation part followed by a Dose Expansion part in ovarian cancer. Each dose level in the Dose Escalation period will be conducted using a standard 3+3 study design in order to determine the safety and tolerability of each dose. For Arm A Dose Escalation, once a dose level has been cleared for safety, that dose level is open to enrollment of up to 9 additional patients who are willing and eligible to undergo tumor biopsy.

Once the expected MTD/RDE has been cleared in Dose Escalation for Arm A, Dose Escalation in Arm B will begin with a dose of 4mg mRNA-2416, 1 dose level lower than the Arm A MTD/RDE according to [Table 1](#).

For both Arms, once the expected MTD/RDE has been cleared in Dose Escalation, Dose Confirmation of the MTD/RDE will be conducted in at least 3 patients with visceral lesions injectable with ultrasound or CT guidance. The purpose of the Dose Confirmation part is to confirm that the dose level determined for patients with accessible lesions is also appropriate for patients with visceral lesions. Dose Confirmation will be conducted in the same fashion as Dose Escalation, as described in Section 8.2.1 and Section 8.4.

For both Arms, once the MTD and/or RDE has been determined in Dose Escalation/Confirmation, patients will be enrolled in an Expansion cohort in order to assess the preliminary anti-tumor activity of mRNA-2416 in ovarian cancer of epithelial origin

The Dose Expansion will consist of 2 investigational groups across the treatment arms summarized as follows and shown in [Figure 1](#):

Arm A: mRNA-2416 alone

[figure not shown]
- Group 1: Ovarian cancer

Arm B: mRNA-2416 in combination with durvalumab

- Group 2: Ovarian cancer

The study schema is presented in [Figure 1](#).

Figure 1: mRNA-2416-P101 Study Schema

1 - Dose Escalation: 3+3 model. DLT window = 1 cycle (28D)

2 - Dose Escalation in Arm B: To begin once the expected MTD/RDE has been cleared in Arm A Dose Escalation

3 - Dose Confirmation: To confirm the MTD/RDE in visceral lesions after clearance of MTD/RDE in accessible lesions

4 - Dose Expansion: Simon two-stage model

8.2.1 ARM A DOSE ESCALATION PERIOD

Dose escalation will be conducted using a standard 3+3 study design in order to determine safety and tolerability of the study therapy (see [Section 8.4](#) for further details). The planned mRNA-2416 starting dose is 1.0 mg (0.5 mL) on Day 1 and Day 15 of 28-day cycles. Patients will be evaluated at the end of the first 28-day period (Cycle 1). A sentinel patient will receive their initial dose of mRNA-2416 1.0 mg intratumoral injection per intratumoral injection criteria ([Section 10.1](#)). Following a 7-day observation period, additional patients may be enrolled in the 1.0 mg cohort. [Table 1](#) describes the 1.0 mg starting dose and other dose levels that may be evaluated during this trial. Subsequent dose cohorts may enroll up to 3 patients at a time. No intra-patient dose escalations may occur.

Table 1: Arm A Provisional Dose Levels

Dose level	Proposed mRNA-2416 Q2W dose
-1	0.5 mg (0.25 mL)
1 (starting dose)	1.0 mg (0.5 mL)
2	2.0 mg (1.0 mL)
3	4.0 mg (2.0 mL)
4	8.0 mg (4.0 mL)

Once a dose level has been cleared for safety, the dose level is open to enrollment of up to an additional 9 patients who are willing and eligible to undergo tumor biopsy for analysis (see details in [Section 8.2.2](#)). Any adverse events among patients in the biopsy enrichment cohorts would be considered in determining an appropriate RDE but will not affect the determination of the MTD. These cohorts are only opened at doses cleared for safety and are separate from the 3 + 3 escalation model described in [Section 8.4.4](#).

Patients must have a superficial tumor lesion amenable to injection. A tumor lesion amenable to injection during the Dose Escalation Period is defined as a superficial tumor lesion that is

- clearly visible or palpable
- can be easily injected without the use of imaging guidance, and
- All lesion(s) targeted for the initial injection must be ≥ 0.5 cm on longest diameter, be at least 5 mm thick, and have distinct borders based on exam or imaging, not close to critical structures such as major vessels, nerves, or airways.

8.2.2 ARM A DOSE ESCALATION BIOPSY COHORT ENRICHMENT

For Arm A Dose Escalation, once a dose level has been cleared for safety, the dose level is open to enrollment of additional patients who are willing and eligible to undergo tumor biopsy. Eligible patients should be enrolled into the highest dose level that has been cleared for safety, providing their injectable tumor volume permits the necessary dose of mRNA-2416 according to [Section 10.1 Table 3](#). For patients whose tumor volume does not support dosing at the highest cleared dose level, participation in a lower dose level is acceptable.

Up to 9 patients can be enrolled into the biopsy cohort at each dose level: 3 patients in Group A, 3 in Group B and 3 in Group C. Enrollment in the Biopsy Cohort Enrichment will continue throughout the conduct of the study until all slots are filled or it is determined additional enrollment is not required. Refer to [Section 10.12](#) for further details on the enrollment in Biopsy Cohort Enrichment.

8.2.3 ARM B DOSE ESCALATION PERIOD

Dose escalation will be conducted using a standard 3+3 study design in order to determine safety and tolerability of the study therapy (see [Section 8.4](#) for further details). In combination with a fixed dose of 1500 mg durvalumab every 4 weeks, the planned mRNA-2416 dose is 4.0 mg (2 mL) on Day 1 and Day 15 of 28-day cycles for Cycle 1, and on Day 1 only for Cycles 2-6. Patients will be evaluated at the end of the first 28-day period (Cycle 1). A sentinel patient will receive their initial dose of mRNA-2416 in combination with durvalumab. Following a 7-day observation period, additional patients may be enrolled in the 4.0 mg cohort. [Table 2](#) describes the 4.0 mg starting dose and other dose levels that may be evaluated during this trial. Subsequent dose cohorts may enroll up to 3 patients at a time. No intra-patient dose escalations may occur.

Table 2: Arm B Provisional Dose Levels

Dose level	Proposed mRNA-2416 dose	Durvalumab dose level
-1	2.0 mg (1.0 mL)	1500 mg
1 (starting dose)	4.0 mg (2.0 mL)	1500 mg
2	8.0 mg (4.0 mL)	1500 mg

8.2.4 DOSE CONFIRMATION IN VISCERAL LESIONS

For both Arms, once the expected MTD/RDE has been cleared in Dose Escalation, Dose Confirmation of the MTD/RDE will be conducted in at least 3 patients with visceral lesions injectable with ultrasound or CT guidance. The purpose of the Dose Confirmation part is to confirm that the dose level determined for patients with accessible lesions is also appropriate for patients with visceral lesions. Dose Confirmation will be conducted in the same fashion as Dose Escalation as described in Section 8.2.1 and Section 8.4. A sentinel patient will receive their initial dose of mRNA-2416 intratumoral injection per intratumoral injection criteria (Section 10.1). Following a 7-day observation period, additional patients may be enrolled in the Dose Confirmation cohort.

8.2.5 ARM A PHASE II DOSE EXPANSION PERIOD

Once the MTD and/or RDE has been determined in Dose Escalation/Confirmation, patients will be enrolled in the Expansion period in order to assess the preliminary anti-tumor activity of mRNA-2416 in ovarian cancer of epithelial origin. The Expansion period will initially enroll 13 evaluable patients, unless enrolling 13 patients is not logistically feasible, in which case enrollment may be stopped before 13 patients are enrolled. If at least 1 patient has an objective response (partial response [PR] or complete response [CR]) per RECIST v1.1 or iRECIST, the sample size may be expanded to 27 evaluable patients. Details of the sample size calculations leading to the patient numbers are provided in Section 13.2.

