7.2 PRIMARY ENDPOINTS

The primary endpoints of the study are as follows:

Phase 1

- Incidence and nature of dose-limiting toxicities (DLTs) with mRNA-2416 alone and in combination with durvalumab
- Incidence, nature, and severity of AEs/serious adverse events (SAEs), graded according to the National Cancer Institute (NCI) Common Terminology Criteria for Adverse Events (CTCAE) Version 4.03 for mRNA-2416 alone and in combination with durvalumab

Phase II

- Assessment of objective response rate of mRNA-2416 alone and in combination with durvalumab in patients with ovarian cancer based on RECIST v1.1

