8.2.6 ARM B PHASE II DOSE EXPANSION PERIOD

Once the MTD and/or RDE has been determined in Dose Escalation/Confirmation, patients will be enrolled in the Expansion period in order to assess the preliminary anti-tumor activity of mRNA-2416 in combination with durvalumab in ovarian cancer of epithelial origin. The Expansion period will initially enroll 15 evaluable patients, unless enrolling 15 patients is not logistically feasible, in which case enrollment may be stopped before 15 patients are enrolled. If at least 2 patients have an objective response (partial response [PR] or complete response [CR]) per RECIST v1.1 or iRECIST, the sample size may be expanded to 41 evaluable patients. Details of the sample size calculations leading to the patient numbers are provided in Section 13.2.

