13.2 SAMPLE SIZE CONSIDERATIONS

No formal sample-size estimation will be performed. The choice of the number of patients will be based on a standard, Phase 1, 3+3 dose escalation design in which 3 to 6 patients are enrolled into each dose cohort.

For the Arm A dose expansion period, the sample size estimation is based on Simon's minimax two-stage design (Richard S, 1989). The null hypothesis that the true overall response rate is 0.05 will be tested, and this design with the sample size of 13 and 14 for the first and second stage, respectively, will provide an overall one-sided alpha value of 0.05 and statistical power of 0.80 when the true overall response rate is 0.20. If there is 1 or more response observed from the 13 subjects in first stage, the study will proceed to the second stage. To account for potential patient drop-out, a total of approximately 30 patients will be enrolled in order to obtain evaluable data from 27 patients. If four or more responses are observed in the 27 evaluable patients, mRNA-2416 will be considered active in ovarian cancer patients, and may warrant further development.

For the Arm B dose expansion period, the sample size estimation is based on Simon's two-stage design (Richard S, 1989). The null hypothesis that the true overall response rate is 0.1 will be tested, and this design with the sample size of 15 and 26 for the first and second stage, respectively, will provide an overall one-sided alpha value of 0.05 and statistical power of 0.80 when the true overall response rate is 0.25. If there is 2 or more responses observed from the 15 patients in first stage, the study will proceed to the second stage. To account for potential patient drop-out, a total of approximately 45 patients will be enrolled in order to obtain evaluable data from 41 patients. If eight or more responses are observed in the 41 evaluable patients, mRNA-2416 in combination with durvalumab will be considered active in ovarian cancer patients, and may warrant further development.

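### The Stage 1 gates in both expansion arms accept a response by RECIST v1.1 or iRECIST, while the primary endpoint is RECIST v1.1 alone, so the futility stop can only be weaker than the Simon designs imply

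*Protocol*

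**What the plan says.** **The gates.** Protocol 8.2.5 enrols 13 evaluable Arm A patients first. With at least one PR or CR "per RECIST v1.1 or iRECIST, the sample size may be expanded to 27 evaluable patients". Protocol 8.2.6 enrols 15 in Arm B. With at least two such responses "per RECIST v1.1 or iRECIST, the sample size may be expanded to 41 evaluable patients". Both sections refer to 13.2 for the calculation.

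**The design.** For Arm A, Protocol 13.2 states: "The null hypothesis that the true overall response rate is 0.05 will be tested". It claims an "overall one-sided alpha value of 0.05 and statistical power of 0.80 when the true overall response rate is 0.20". Its gate reads: "If there is 1 or more response observed from the 13 subjects in first stage, the study will proceed to the second stage". Arm B has a null rate of 0.10, an alternative of 0.25, stages of 15 and 26, and a gate of 2 responses. The final rules are at least 4 of 27 and at least 8 of 41. SAP 4.1 repeats the stage sizes and gates but omits the final cut-offs. Neither 13.2 nor SAP 4.1 names a response criterion.

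**The endpoint.** Protocol 7.2 sets the Phase II primary endpoint as objective response rate "in patients with ovarian cancer based on RECIST v1.1". SAP 3.2.1 agrees. The immune-related criteria in Protocol 7.6 and SAP 3.2.3 are irRC and LYRIC, and they are exploratory. iRECIST appears only in the two gate sentences. It is absent from the abbreviations, the endpoints, Appendices C and D, and the SAP.

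**The concern.** A Simon design is calibrated for one response variable. Its null rate, alternative and cut-offs all refer to the same count. Here the primary endpoint points to RECIST v1.1, but the gate that would be operated admits a second criterion that the calculation does not cover.

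The first stage exists to stop an inactive regimen before another 14 (Arm A) or 26 (Arm B) patients receive intratumoral injections and protocol-required biopsies. A looser gate weakens that protection. A continuation decision that rested on an iRECIST response would also be hard to reproduce, because the protocol does not define the criterion and sites assess RECIST 1.1 and irRC/LYRIC (Protocol 10.10, SAP 8).

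A second gap follows. If the final cut-offs were read with the same two criteria as the gate, the stated alpha would no longer hold.

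**Working it through.** **Inputs (Protocol 13.2).**
- Arm A: p0 = 0.05, p1 = 0.20, n1 = 13, n2 = 14. Continue at 1 or more; declare activity at 4 or more of 27.
- Arm B: p0 = 0.10, p1 = 0.25, n1 = 15, n2 = 26. Continue at 2 or more; declare activity at 8 or more of 41.
- Assumed, because the documents give no figure: *d*, the probability of a response by iRECIST but not by RECIST v1.1.

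**Step 1: reproduce the plan (d = 0), by exact binomial.**
- Arm A stopping probability under the null: 0.95^13 = 0.513. Expected N = 13 + (1 − 0.513) × 14 = 19.8.
- Arm B: 0.9^15 + 15 × 0.1 × 0.9^14 = 0.549. Expected N = 15 + (1 − 0.549) × 26 = 26.7.
- Attained alpha and power: 0.0416 and 0.801 (Arm A), 0.0430 and 0.803 (Arm B). Both arms meet the stated 0.05 and 0.80. An exhaustive search confirms that 13/27 is the minimax design for Arm A.

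**Step 2: direction.** The patients who respond by either criterion include all who respond by RECIST v1.1. The Stage 1 count therefore cannot be lower, and the stopping probability cannot be higher. It is strictly lower if any iRECIST-only response is possible.

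**Step 3: size.** Replace p0 by p0 + d in the stopping probability. The RECIST v1.1 rate stays at p0. Expected N treats passing the gate as continuing.

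| d (percentage points) | Arm A: stop under null | Arm A: expected N | Arm B: stop under null | Arm B: expected N |
|---|---|---|---|---|
| 0 | 0.513 | 19.8 | 0.549 | 26.7 |
| 1 | 0.447 | 20.7 | 0.497 | 28.1 |
| 3 | 0.338 | 22.3 | 0.401 | 30.6 |
| 5 | 0.254 | 23.4 | 0.319 | 32.7 |

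**Step 4: alpha and power when the final count is RECIST v1.1.** In Arm A, the rejection probability is that of a single-stage rule (4 or more of 27) minus the part lost by stopping early:
- Single-stage alpha is 0.04374, and P(4 or more of 14 at 0.05) = 0.00418.
- As designed: 0.04374 − 0.5133 × 0.00418 = 0.0416.
- At d = 5 points: 0.04374 − 0.2542 × 0.00418 = 0.0427.

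Arm B, by summing over the Stage 1 outcomes, goes from 0.0430 to 0.0453 at 5 points. The single-stage values, 0.0437 and 0.0477, are ceilings for any d. Power at 5 points rises from 0.801 to 0.811 (Arm A) and from 0.803 to 0.824 (Arm B).

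**Step 5: if the combined criterion were also used for the final count.** The two-stage rule then operates at p0 + d. The chance of declaring activity when the RECIST v1.1 rate equals the null is:

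| d (percentage points) | Arm A | Arm B |
|---|---|---|
| 1 | 0.072 | 0.068 |
| 3 | 0.159 | 0.142 |
| 5 | 0.271 | 0.244 |

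**The case against.** **The size is unknown and may be small.** This stands. In Arm A, an excess of 3 to 5 points would make iRECIST-only responses 60 to 100% as frequent as ordinary responses under the null (3/5 and 5/5). Protocol 10.10 ends study therapy once progression is confirmed by irRC, which narrows the window for a late immune-only response. At 1 point the cost is about one expected patient per arm (20.7 − 19.8 = 0.9 and 28.1 − 26.7 = 1.4). A reader might infer from the lower rows of the table that the stop is badly compromised. The documents do not support that, because they contain no figure for the excess.

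**The looser gate may be deliberate.** The protocol expects pseudoprogression and allows treatment past RECIST progression (10.5, 10.10). A response after apparent progression is still tumour shrinkage, and the looser gate gains a little power. The aim is legitimate. It would still need a defined criterion, with null and alternative rates and cut-offs derived for it.

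**The gate is permissive.** Sections 8.2.5 and 8.2.6 allow expansion without requiring it, so the sponsor could still stop. That discretion does not restore a prespecified stop, and it conflicts with 13.2 and SAP 4.1, where continuation is mandatory.

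**iRECIST may be a slip for irRC,** which Appendix C does define. If so, the audit problem reduces to a wording correction, but two criteria would still be admitted at the gate.

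**Conclusion.** The inconsistency is real, and its direction is certain: both futility stops can only be weaker than designed. The size depends on an assumed excess. From 0 to 5 percentage points, the null stopping probability runs from 0.513 down to 0.254 in Arm A and from 0.549 down to 0.319 in Arm B.

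Two stronger readings should be avoided:
- A reader might infer that the gate itself inflates the type I error. It does not if the final count uses RECIST v1.1: at 5 points alpha is 0.043 (Arm A) and 0.045 (Arm B). The stated level is exceeded only if the combined criterion is carried into the final count, and no passage says that it would be.
- A reader might infer that the Simon sections specify RECIST v1.1. They name no criterion. It is a sound inference from the primary endpoint, but not a statement in the text.

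The alpha result therefore depends on something the plan leaves unsaid. That makes the unnamed final-count criterion as important to settle as the gate wording. The change should be made, but the point does not invalidate the design.

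**What to change.** 1. Protocol 8.2.5 and 8.2.6: delete *or iRECIST*, so that Stage 1 counts RECIST v1.1 responses.
2. Protocol 13.2 and SAP 4.1: state that the Stage 1 counts (at least 1 of 13, at least 2 of 15) and the final counts (at least 4 of 27, at least 8 of 41) all use RECIST v1.1 responses as defined for the primary response rate. Add the final cut-offs to SAP 4.1, which omits them.
3. Reconcile the optional expansion in 8.2.5 and 8.2.6 with the mandatory continuation in 13.2 and SAP 4.1.
4. Report irRC responses descriptively at the Stage 1 look.

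The cost is a few words in a protocol amendment and a sentence or two in the SAP. The sponsor loses some latitude to continue on an immune-criteria response, and forgoes the small power gain of the looser gate (at an excess of 5 points, about 0.01 in Arm A and 0.02 in Arm B). If that latitude is wanted, the alternative is to define the combined endpoint and re-derive the null rate, alternative rate and cut-offs for it.

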8.2.6 ARM B PHASE II DOSE EXPANSION PERIOD

Once the MTD and/or RDE has been determined in Dose Escalation/Confirmation, patients will be enrolled in the Expansion period in order to assess the preliminary anti-tumor activity of mRNA-2416 in combination with durvalumab in ovarian cancer of epithelial origin. The Expansion period will initially enroll 15 evaluable patients, unless enrolling 15 patients is not logistically feasible, in which case enrollment may be stopped before 15 patients are enrolled. If at least 2 patients have an objective response (partial response [PR] or complete response [CR]) per RECIST v1.1 or iRECIST, the sample size may be expanded to 41 evaluable patients. Details of the sample size calculations leading to the patient numbers are provided in Section 13.2.

8.2.7 PHASE II DOSE EXPANSION PERIOD STOPPING RULES

Further computations of the DLT rate will be performed during the Expansion Period in order to incorporate study stopping rules. During the Expansion Period, the DLT rate will be calculated as events occur. The DLT rate will be defined as the ratio of the total number of patients with a DLT at the MTD/RDE divided by the total number of patients enrolled at that dose level who are evaluable for DLT (for evalutability see Section 8.4.4).

If the DLT rate is $\geq 33\%$, a temporary study suspension of enrollment at the MTD/RDE will be required in order to perform a thorough and in-depth review of the available safety information to determine whether additional patients should be enrolled at that dose level. The SRC may decide to enroll 3 more patients at the MTD/RDE and review the DLT rate again once those patients become evaluable for DLT. Alternatively, if the SRC determines that there is a reasonable probability that the DLT rate will remain higher than 33% with further enrollment of patients at that dose level, then the SRC may decide to stop enrollment at the MTD/RDE and permit expansion of a dose level lower than the MTD/RDE. Enrollment at the new RDE will be subject to the same enrollment and stopping rules as expansion at the MTD/RDE.

In addition, any Grade 4 toxicity related to mRNA-2416 during the Expansion Period will require a temporary suspension of expansion and review by the SRC. A drug-related death at any time during the study would result in study pause and expedited notification to FDA per 21 CFR 312.32

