8.4.3 DEFINITION OF MTD

The MTDs will be defined as the highest dose of mRNA-2416 alone and in combination with durvalumab at which a DLT has been seen in less than 2 of 6 patients (<33%) during the first 28-days of study therapy.

If 2 or more adverse events that meet the definition of a DLT as defined in [Section 8.4.2](#), are observed beyond the first 28 days of study therapy within a dose escalation cohort, further enrollment may be held, pending safety analysis of the events by the SRC. These events will not affect the determination of the MTD but will be used in determining the appropriate RDE.

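### The Expansion DLT suspension rate names neither period nor arm, so DLT-evaluable Phase I patients at the same dose dilute an Expansion signal, chiefly in Arm A

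*Protocol*

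**What the plan says.** Section 8.2.7 of the protocol sets the rule: "If the DLT rate is $\geq 33\%$, a temporary study suspension of enrollment at the MTD/RDE will be required". The numerator is given by "the ratio of the total number of patients with a DLT at the MTD/RDE", and it is "divided by the total number of patients enrolled at that dose level who are evaluable for DLT". Timing is also stated: "During the Expansion Period, the DLT rate will be calculated as events occur". Evaluability is taken from Section 8.4.4, which asks for minimum Cycle 1 exposure plus either 28 days of follow-up or a DLT. It does not exclude Phase I patients.

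Phase I places patients at the same dose in three ways.

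- **Escalation:** 3 to 6 patients per dose cohort (Section 13.2). The MTD requires fewer than 2 DLTs in 6 (Section 8.4.3).
- **Biopsy enrichment, Arm A only:** "Up to 9 patients can be enrolled into the biopsy cohort at each dose level" (Section 8.2.2). Adverse events in these patients "would be considered in determining an appropriate RDE but will not affect the determination of the MTD" (Section 8.2.1).
- **Dose Confirmation, both arms:** "Dose Confirmation of the MTD/RDE will be conducted in at least 3 patients with visceral lesions" (Section 8.2.4).

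The SAP defines DLTs and plans a table of them (Section 9.1.1). It neither restates nor clarifies the suspension rule.

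**The concern.** The Phase I patients who enter the ratio are not a neutral background. The dose reached Expansion because its escalation cohort had at most 1 DLT in 6, so the starting rate is low by selection. Escalation patients had superficial lesions and any solid tumor or lymphoma. Expansion patients have ovarian cancer with superficial or visceral lesions, and the protocol runs Dose Confirmation precisely because it does not assume that the dose carries over to visceral lesions.

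If toxicity in Expansion is clearly above the 33% limit, the ratio can stay below the limit for many patients because the denominator already holds largely DLT-free people. Enrollment would then continue without the mandatory review. Section 8.2.7 also does not say which arm's patients or DLT definition apply, although Section 8.4.2 gives the arms different DLT criteria.

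**Working it through.** **1. The plan's own limit.** 2/6 = 33.3% meets the 33% limit and 1/6 = 16.7% does not, so Sections 8.2.7 and 8.4.3 agree. The protocol states no operating characteristics for the Expansion rule.

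**2. Phase I starts (assumed from the cohort limits; actual counts are not in the documents).**

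- 1/18, Arm A: 6 escalation + 9 enrichment + 3 confirmation, one DLT.
- 1/9, either arm: 6 escalation + 3 confirmation, one DLT.
- 0/21, Arm A outer bound: 6 + 9 + 6, no DLT.
- 0/12, Arm B outer bound: 6 + 6, no DLT.

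**3. Trigger.** With d0 DLTs among N0 Phase I patients, and x DLTs among n Expansion patients, the rule fires when (d0 + x)/(N0 + n) ≥ 1/3, that is, when x ≥ (N0 + n)/3 − d0.

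- 1/18, n = 13: 31/3 − 1 = 9.3, so 10 DLTs.
- 1/9, n = 13: 22/3 − 1 = 6.3, so 7.
- 0/21, n = 13: 34/3 = 11.3, so 12.
- Expansion alone, n = 13: 13/3 = 4.3, so 5.

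These are the counts at patient 13 only. The rate is recalculated at each event, so from 1/18 it can also fire at 8 of 8 (9/26 = 34.6%) or 9 of 12 (10/30 = 33.3%).

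**4. Probability of firing.** Let P(n, x) be the probability of x DLTs after n patients without having fired. Then P(n, x) = (1 − p)·P(n−1, x) + p·P(n−1, x−1), and any state that meets the trigger is moved to fired. This is exact and allows for every earlier crossing. With p = 0.50 (an assumption):

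| Arm and start | by stage 1 | by full size |
|---|---|---|
| A, 1/18 | 7.5% (13) | 54% (27) |
| A, 1/9 | 66% (13) | 92% (27) |
| A, 0/21 | 0.3% (13) | 24% (27) |
| B, 0/12 | 32% (15) | 88% (41) |
| B, 1/9 | 75% (15) | 97% (41) |

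At p = 0.60 the figures by 13 patients are 23% from 1/18 and 87% from 1/9.

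**5. Expansion patients alone, checked after each patient from the 6th.** By 13 patients this fires 13%, 41%, 75% and 96% of the time at true rates of 10%, 20%, 33% and 50%. At 20% it reaches 44% by 27. If the check is made only when a new DLT occurs, the four figures by 13 patients are 8%, 32%, 69% and 95%.

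**6. Either rate.** The cumulative rate is a weighted average of a start below 1/3 and the Expansion rate. From the 6th patient on, it cannot reach 1/3 unless the Expansion rate already has. Before the 6th, of the four starts only 1/9 can fire. It needs x ≥ 2 + n/3, so at least 3 DLTs, which is already at least 3/6 at patient 6. For these starts, the after-each-patient figures in step 5 therefore also hold for review on either rate.

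**The case against.** The strongest reply concerns the enrichment patients. Section 8.2.1 keeps those cohorts apart from the 3+3 in Section 8.4.4, and Section 8.4.4 speaks of evaluability for dose determination. A reader could exclude them on that basis, and the Arm A start falls to 1/9. Nine is also a ceiling: Section 8.2.2 allows a lower dose where tumor volume is insufficient, and Table 3 allows 4.0 mL in a single lesion only above 5 cm. This stands as a limit on size. It does not settle the text, since Section 8.2.7 counts patients enrolled at the dose level and Section 8.2.2 directs enrichment patients to the highest cleared dose when volume permits.

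Other safeguards remain. A related Grade 4 toxicity or a drug-related death has its own trigger, DLTs are notified to the sponsor immediately, and the SRC meets as needed. They narrow the gap to DLTs below Grade 4. The documents give no figure for what share of DLTs that is. Section 6.2 describes the common reactions among the first 32 patients as mild to moderate apart from one Grade 3 injection-related reaction, so 50% is a stress case and not a forecast.

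A reader might infer that the arms are pooled at a shared 8.0 mg and that the rule can then never fire in Arm B. The documents do not support this. Table 2 defines Arm B levels as mRNA-2416 plus durvalumab, Section 8.4.3 refers to separate MTDs, and Section 8.4.2 has separate DLT criteria, so the arm's own level is the natural reading. Even pooled (18 + 27 from Arm A, 9 from Arm B Phase I, 2 earlier DLTs, every Arm B Expansion patient with a DLT), the ratio is 17/69 = 24.6% after 15 patients but reaches 26/78 = 33.3% at patient 24 of 41.

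**Conclusion.** The concern holds for Arm A as the rule is written. At a true 50% Expansion DLT rate, the chance that the mandatory review is triggered within the 13 stage 1 patients ranges from 0.3% (0/21) through 7.5% (1/18) to 66% (1/9), against 96% on Expansion patients alone from the 6th. Over the full 27 patients the two middle starts recover to 54% and 92%. Arm B counted alone is delayed and not disabled.

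It would go too far to call the rule inert. That description fits only the heaviest Arm A starts during stage 1. The result rests on the assumed Phase I counts, on enrichment patients being counted for the 1/18 and 0/21 starts, and on the assumed 50% rate. The missing arm is an ambiguity to close, not evidence that pooling is intended.

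**What to change.** In Section 8.2.7, state that the DLT rate is computed separately for Arm A and Arm B, consistent with Sections 8.4.2 and 8.4.3 and Table 2. State whether enrichment patients count. Report the rate to the SRC both cumulatively and for Expansion patients alone, with the existing 33% limit prompting SRC review on either. The sponsor should set the minimum number of evaluable Expansion patients, say whether the check follows each patient or each DLT, and give the operating characteristics.

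The cost is a few sentences in an amendment and one extra line per arm in the SRC report. No patients are added. The downside is more temporary pauses: if checked after each patient from the 6th, about 13% of trials by 13 patients at a true 10% rate and about 41% at 20%, in each arm. A later starting point would lower these figures at the price of slower detection, which is why the choice belongs to the sponsor.
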